Appendix 3 Temozolomide dosing (100mg/m²/day) Nomogram

Temozolomide is dosed based on BSA. The dose should be rounded off to the nearest 5 mg (round 2.5 mg down). For patients with BSA <0.5 m², dosing is based on body weight (kg).

For patients with a BSA < 0.5 m²: Use **3.3 mg/kg**.

Examples:

Patient has a BSA of 0.3 m² and weighs 5 kg. Patient administered dose = 5 kg x 3.3 mg/kg = 16.5 mg

Patient has a BSA of 0.66 m². Calculated dose is 0.66 m² x 100 mg/m² = 66 mg/day;
Administered dose = 65 mg temozolomide/day.

BSA (m ²)	Calculated daily dose (mg)	Administered daily dose (mg)
< 0.50	3.3 mg/kg	3.3 mg/kg
0.50-0.52	50-52	50
0.53-0.57	53-57	55
0.58-0.62	58-62	60
0.63-0.67	63-67	65
0.68-0.72	68-72	70
0.73-0.77	73-77	75
0.78-0.82	78-82	80
0.83-0.87	83-87	85
0.88-0.92	88-92	90
0.93-0.97	93-97	95
0.98-1.0	98-100	100
1.01-1.05	100-105	105
1.06-1.14	105-114	110
1.15-1.24	115-124	120
1.25-1.34	125-134	130
1.35-1.44	135-144	140
1.45-1.54	145-154	150
1.55-1.64	155-164	160
1.65-1.74	165-174	170
1.75-1.84	175-184	180
1.85-1.94	185-194	190
1.95-2.00	195-200	200
> 2.0	> 200	200

Appendix 4 Nomogram for Reduced Dosing (80 mg/m²/day) of Temozolomide

Temozolomide is dosed based on BSA for patients whose BSA is at least 0.5 m². For these patients, doses are rounded to the nearest 5 mg. For patients with BSA <0.5 m², dosing is based on body weight (kg). If unacceptable temozolomide associated specific toxicities occur (see Section 8.4.4), a 20% dose reduction should be applied (80mg/m²/day). If the toxicity recurs despite the dose reduction a second 20% dose reduction (60 mg/m²/day) may be applied (see [Appendix 5](#))

For patients with a BSA < 0.5 m²: Use **2.6 mg/kg**.

Examples:

- For a patient with a BSA of 0.3 m² and weighs 5 kg, the calculated dose is 5 kg x 2.6 mg/kg = 13.0 mg
- For a patient with a BSA of 0.66 m², the calculated dose = 52.8 mg/dose; administered dose = 55 mg temozolomide/dose.

BSA (m ²)	Calculated daily dose (mg)	Administered daily dose (mg)
0.2-0.49	2.6 mg/kg	2.6 mg/kg
0.50 - 0.53	40 - 42	40
0.54 - 0.59	43 - 47	45
0.60 -0.65	48 - 52	50
0.66-0.71	53 -57	55
0.72-0.78	58 - 62	60
0.79-0.84	63 - 67	65
0.85-0.90	68 - 72	70
0.91-0.96	73 - 77	75
0.97-1.03	78 - 82	80
1.04-1.09	83 - 87	85
1.10-1.15	88 - 92	90
1.16-1.21	93 - 97	95
1.22-1.28	98 - 102	100
1.29-1.34	103 -107	105
1.35-1.40	108 - 112	110
1.41-1.46	113 - 117	115
1.47-1.53	118 - 122	120
1.54-1.59	123 - 127	125
1.60-1.65	128 - 132	130
1.66-1.71	133 - 137	135
1.72-1.78	138 - 142	140
1.79-1.84	143 - 147	145
1.85-1.90	148 - 152	150
1.91-1.96	153 - 157	155
>1.96	>157	160

Appendix 5 Nomogram for Reduced Dosing (60 mg/m²/day) of Temozolomide

Temozolomide is dosed based on BSA for patients whose BSA is at least 0.5 m². For these patients, doses are rounded to the nearest 5 mg. For patients with BSA <0.5 m², dosing is based on body weight (kg). If unacceptable temozolomide associated specific toxicities recur despite the first dose reduction by 20% (see Section 8.4.4), a second 20% dose reduction (60 mg/m²/day) should be applied.

For patients with a BSA < 0.5 m²: Use **2.0 mg/kg**.

Examples:

- For a patient with a BSA of 0.3 m² and weighs 5 kg, the calculated dose is 5 kg x 2.0 mg/kg = 10.0 mg
- For a patient with a BSA of 0.66 m², the calculated dose = 39.6 mg/dose; administered dose = 40 mg temozolomide/dose.

BSA (m ²)	Calculated daily dose (mg)	Administered daily dose (mg)
0.2-0.49	2.0 mg/kg	2.0 mg/kg
0.50 - 0.54	30 - 32	30
0.55 - 0.62	33 - 37	35
0.63 -0.70	38 - 42	40
0.71-0.79	43 - 47	45
0.80-0.87	48 - 52	50
0.88-0.95	53 -57	55
0.96-1.04	58 - 62	60
1.05-1.12	63 - 67	65
1.13-1.20	68 - 72	70
1.21-1.29	73 - 77	75
1.30-1.37	78 - 82	80
1.38-1.45	83 - 87	85
1.46-1.54	88 - 92	90
1.55-1.62	93 - 97	95
1.63-1.70	98 - 102	100
1.71-1.79	103 -107	105
1.80-1.87	108 - 112	110
1.88-1.95	113 - 117	115
>1.95	>117	120

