7.12 Premature Discontinuation of Treatment

General discontinuation criteria

A patient should be discontinued from treatment with all IMPs if any of the following situations occur:

1. Grade 4 anaphylaxis related to naxitamab
2. Grade 3 anaphylaxis related to naxitamab not responding to medical intervention at the discretion of the investigator
3. Grade 4 sensory neuropathy or Grade 3 sensory neuropathy that interferes with daily activities for more than 2 weeks at the discretion of the investigator
4. CTCAE Grade 3 pain unresponsive to maximum supportive measures at the discretion of the investigator
5. Grade 4 bronchospasm
6. Grade 3 bronchospasm not responding to medical intervention at the discretion of the investigator
7. Posterior reversible encephalopathy syndrome (PRES)
8. The investigator judges it necessary for medical reasons/non-compliance
9. The patient receives prohibited therapy and/or procedures during the trial, see Section [8.4.8](#)
10. Pregnancy
11. Patient/legal guardian withdraw consent to treatment
12. PD

Discontinuation criteria for IT

A patient should be discontinued from IT treatment if any of the following situations occur:

1. If the patient experiences neutropenia that causes a delay \geq 14 days after the first dose reduction by 20% of irinotecan and the second dose reduction by 20% of temozolomide
2. If the patient experiences thrombocytopenia that causes a delay \geq 14 days after the first dose reduction by 20% of irinotecan and the second dose reduction by 20% of temozolomide
3. If the patient does not meet the criteria to start the next cycle within 21 days after the planned subsequent cycle start date
4. Recurrence of \geq Grade 3 diarrhea despite maximal use of anti-diarrheals, prophylactic antibiotics, and a dose reductions of irinotecan of 20%
5. Recurrence of \geq Grade 3 regimen-related nausea and/or vomiting despite optimization of anti-emetic drugs and a dose reduction of IT by 20%
6. If \geq Grade 3 regimen-related dehydration recurs and persists for >3 days despite a dose reduction of IT by 20%

Discontinuation criteria for GM-CSF

A patient should be discontinued from GM-CSF treatment if any of the following situations occur:

1. Injection site reactions \geq CTCAE Grade 3
2. Allergic reactions (including anaphylactic reactions) \geq CTCAE Grade 3

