8.4.4.2 Management of non-hematologic toxicities

Patients who have experienced non-hematologic toxicity should receive dose-reduction of IT treatment as described in the following sections at the discretion of the investigator.

Dose modification for diarrhea

See Section [8.4.3](#) for patient/family instructions for supportive care measures for patients who develop therapy-associated diarrhea.

- If \geq CTCAE Grade 3 therapy-associated diarrhea is experienced by a patient despite maximal use of anti-diarrheal medications and appropriate use of prophylactic antibiotics, the dose of irinotecan should be reduced by 20% for subsequent cycles (i.e., irinotecan dose $40.0 \text{ mg/m}^2/\text{day}$)
- For treatment related diarrhea requiring discontinuation of IT (please refer to Section [7.12](#))

An IT cycle should not be initiated until treatment-related diarrhea is recovered to \leq CTCAE grade 1.

Dose modifications for nausea and vomiting

- For patients with \geq CTCAE Grade 3 regimen-related nausea and/or vomiting adjustments in the anti-emetic regimen should be made during the next cycle of therapy
- If \geq CTCAE Grade 3 regimen-related nausea and/or vomiting recurs despite optimized anti-emetic usage, doses of IT should be reduced by 20% for subsequent cycles (ie, irinotecan dose $40 \text{ mg/m}^2/\text{day}$; for temozolomide see dose reduction nomogram in [Appendix 4](#))
- For \geq CTCAE Grade 3 regimen related nausea and/or vomiting requiring discontinuation of IT (please refer to Section [7.12](#))

Dose modifications for dehydration

- If dehydration is related to diarrhea or nausea/vomiting, the guidance in the preceding section should be followed
- If regimen-related \geq CTCAE Grade 3 dehydration persists for > 3 days in the absence of significant diarrhea or nausea/vomiting, doses of IT should be reduced by 20% for subsequent cycles (i.e., irinotecan dose $40 \text{ mg/m}^2/\text{day}$; for temozolomide see dose reduction nomogram in [Appendix 4](#))
- For recurrent \geq CTCAE Grade 3 regimen-related dehydration requiring discontinuation of IT, please refer to Section [7.12](#))

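### For recurrent nausea/vomiting or dehydration, Appendices 4 and 5 give a second temozolomide reduction where Section 7.12 stops irinotecan/temozolomide

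*Combined protocol and SAP*

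**What the plan says.** Protocol Section 8.4.4.2 sets the first step. For nausea/vomiting it states that if Grade 3 or higher "regimen-related nausea and/or vomiting recurs despite optimized anti-emetic usage, doses of IT should be reduced by 20% for subsequent cycles". The dehydration rule has the same 20% reduction, once Grade 3 or higher dehydration has persisted for more than 3 days. Both rules send the site to Appendix 4 for the temozolomide dose, and both have a separate bullet that refers discontinuation of IT to Section 7.12.

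Section 7.12 opens its IT list with "A patient should be discontinued from IT treatment if any of the following situations occur". Criterion 5 is recurrence of Grade 3 or higher "regimen-related nausea and/or vomiting despite optimization of anti-emetic drugs and a dose reduction of IT by 20" percent. Criterion 6 applies if Grade 3 or higher "regimen-related dehydration recurs and persists for >3 days despite a dose reduction of IT by 20" percent.

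Appendix 4, where Section 8.4.4.2 has sent these patients, adds: "If the toxicity recurs despite the dose reduction a second 20% dose reduction (60 mg/m²/day) may be applied". Appendix 5 has the same trigger with a firmer verb. Its sentence begins "If unacceptable temozolomide associated specific toxicities recur despite the first dose reduction by 20% (see Section 8.4.4), a second 20% dose reduction" and its instruction in full is "a second 20% dose reduction (60 mg/m²/day) should be applied". Each appendix points to Section 8.4.4 without naming a subsection or a type of toxicity.

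**The concern.** A site treating a patient whose nausea/vomiting has returned after the first reduction has two instructions. On the nomogram page, it finds a second temozolomide step and the patient stays on the 21-day four-drug regimen. In Section 7.12, it finds that IT should stop, and under Section 7.2.1 the patient is then offered naxitamab + GM-CSF alone in 28-day cycles. No clause gives the body text precedence over the appendices.

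Two things are at stake. Patients with the same history could be dosed differently at different sites. And Section 12.13 plans to analyse the proportion of patients who discontinue IT for unacceptable toxicity and then receive naxitamab + GM-CSF alone, and the time to that discontinuation. Both results would partly reflect which page a site consulted.

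**Working it through.** No power or sample-size figure is involved. The check is to set the passages side by side, with a little dose and frequency arithmetic.

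**1. The dose steps agree with each other.** From the 100 mg/m²/day start, the first step is 100 − 20 = 80 and the second 80 − 20 = 60 mg/m²/day. Both reductions are 20% of the starting dose; 20% off 80 would give 64. Section 8.4.4.1 and Appendices 4 and 5 all use 60, so the level itself is not in dispute.

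**2. What each place says when toxicity returns after the first reduction.**

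| Recurrent toxicity | Section 8.4.4 | Appendices 4 and 5 | Section 7.12, IT criteria |
|---|---|---|---|
| Neutropenia or thrombocytopenia with delay of 14 days or more | Second step: temozolomide 60, irinotecan 40 mg/m²/day (8.4.4.1) | Second step | Stop only after the second step (1, 2) |
| Diarrhea, Grade 3 or higher | Irinotecan reduction only; no link to the nomograms | Not reached | Stop after one irinotecan reduction (4) |
| Nausea/vomiting, Grade 3 or higher | No second step; refers to 7.12 | Second step | Stop (5) |
| Dehydration, Grade 3 or higher, lasting more than 3 days | No second step; refers to 7.12 | Second step | Stop (6) |
| Dehydration, Grade 3 or higher, resolving within 3 days | No second step | Second step, on the literal wording | Criterion 6 not met |

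The rows for nausea/vomiting and for dehydration lasting more than 3 days contain the conflict. The hematologic rows agree in substance, and diarrhea is untouched.

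There is also a gap. In Section 8.4.4.1 the second temozolomide step comes with the first irinotecan reduction. After nausea/vomiting or dehydration, irinotecan is already at 40 mg/m²/day, and no passage says what happens to it at a second step.

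**3. What differs between the two routes.** Doses are from Sections 7.2.1 and 8.4.4 and Appendix 2.
- Staying on IT: temozolomide 60 × 5 = 300 mg/m² per 21-day cycle, with irinotecan 40 × 5 = 200 mg/m² if it is left unchanged (an assumption, given the gap above).
- Stopping IT: none of either drug. Naxitamab goes from 4 × 2.25 = 9 mg/kg per 3 weeks (3.0 mg/kg/week) to 3 × 3.0 = 9 mg/kg per 4 weeks (2.25 mg/kg/week). GM-CSF goes from 5 × 250 = 1,250 to 5 × 250 + 5 × 500 = 3,750 µg/m² per cycle.

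**4. How early the conflict can arise.**
- Dehydration: event in cycle 1, reduced dose in cycle 2, recurrence in cycle 2. The first full cycle affected is cycle 3.
- Nausea/vomiting: event in cycle 1, anti-emetic change in cycle 2, recurrence and then reduced dose in cycle 3, recurrence again. The first full cycle affected is cycle 4.

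The primary endpoint counts a response at any time up to completion of four cycles, and the first assessment is after cycle 2.

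**5. How often.** Section 4.3.4 summarises two naxitamab + IT series of 46 and 44 patients, given temozolomide at 150 mg/m²/day. Apart from myelosuppression, diarrhea, pain and hypertension, it reports no related toxicity above Grade 2. Read literally, that is zero cases of related Grade 3 or higher nausea/vomiting or dehydration. Using only the 46-patient series, in case the two overlap, the one-sided 95% upper bound for 0/46 is 1 − 0.05^(1/46) = 0.063. In 52 patients, 0.063 × 52 = 3.3. That bounds a first event. Reaching the conflict takes one further episode for dehydration and two for nausea/vomiting.

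**The case against.** The strongest reply is that the operative text already gives one route. Only Section 8.4.4.1 cites Appendix 5 or the 60 mg/m² dose. Section 8.4.4.2 uses Appendix 4 for the 80 mg/m² dose and then defers to Section 7.12. Section 7.12 makes the same distinction: its hematologic criteria mention a second temozolomide reduction, whereas criteria 5 and 6 mention a single IT reduction. The appendix term, toxicities specific to temozolomide, also differs from the regimen-related events of Section 8.4.4.2. A careful site would probably end at Section 7.12.

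This makes a hematologic-only reading plausible, and it lowers the chance of error. It does not settle the text. Section 8.4.4.2 places nausea/vomiting and dehydration patients on the Appendix 4 page, whose recurrence sentence makes no exception for them, and Appendix 5 carries the same *should* as Section 7.12.

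The *may*/*should* difference is largely editorial, because Sections 8.4.4.1 and 8.4.4.2 both leave dose reduction to the investigator's discretion.

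A reader might infer that a material share of the trial is exposed, say 5–15% of 52, or about 3–8 patients. The documents do not support that: even the upper bound in the working is about 3 patients with a first event. A reader might also infer a threat to the primary endpoint. With cycle 3 or 4 as the earliest full cycle affected, and responses counted from the cycle 2 assessment, that does not follow.

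**Conclusion.** The inconsistency is real and narrow. For Grade 3 or higher regimen-related nausea/vomiting that recurs after the 20% IT reduction, and for such dehydration that recurs and lasts more than 3 days, the appendices and Section 7.12 give incompatible instructions. It does not extend to every recurrence of dehydration, to diarrhea or to the hematologic rules.

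Few patients are likely to be affected, and the effect on the response rate is marginal. This rests on the summary-level safety statement in Section 4.3.4 carrying over to this trial; the documents give no direct frequency for these recurrences. The main consequences are non-uniform dosing between sites and inconsistent inputs to the Section 12.13 analyses of IT discontinuation, where even a few patients classified by different rules would blur a small count.

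**What to change.** Reconcile Appendices 4 and 5 with Sections 8.4.4.1, 8.4.4.2 and 7.12. In both appendices, name the toxicities to which the second-step sentence applies, and check that Section 7.12 says the same for each. Use one verb, *may* or *should*, in both. If the second step is meant to cover any non-hematologic toxicity, state what happens to irinotecan at that step. Which clinical rule applies is for the sponsor to decide.

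The cost is a few sentences in two appendices and a cross-check of Sections 7.12 and 8.4.4, as part of a protocol amendment. It changes no data collection and no sample size.

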Appendix 6 Temozolomide 10 mg/mL suspension

Preparation of oral suspension of Temozolomide⁴⁹:

Recipe for 100 mL	
Temozolomide (from 10 Temodar 100 mg capsules)	1,000 mg
Povidone K-30	500 mg
Anhydrous citric acid	25 mg
Purified water	1,5 mL
Ora-Plus	50 mL
Ora-Sweet or Ora-Sweet SF qs	100 mL

Note: It is necessary to wear suitable protective garb and to perform this procedure in a fume hood. The suspension must be administered at the trial site.

1. Empty the contents of 10 temozolomide 100 – mg capsules in a glass mortar of sufficient size
2. Weigh 500 mg of povidone K-30 powder and add to the mortar
3. Triturate to assure thorough mixing and that the mixture is reduced to a fine powder
4. Dissolve 25 mg of anhydrous citric acid and purified water
5. Add the mixture of anhydrous citric acid and purified water to the mortar to wet the powder
6. Mix thoroughly to form a uniform paste
7. Add a small amount of Ora-Plus suspension vehicle to the triturated paste with thorough mixing to ensure a uniform mixture
8. Add the balance of the Ora-Plus suspension vehicle with thorough mixing to ensure a uniform mixture
9. Transfer the resulting mixture to a glass graduated cylinder
10. Rinse the mortar and pestle with small aliquots of the appropriate syrup (Ora-Sweet or Ora-Sweet SF); repeat the rinsing three times
11. Add an additional quantity of the appropriate syrup vehicle to the bottle to bring the final volume to 100 mL and shake the resulting suspension well
12. Package in amber plastic prescription bottles and label the containers with “Shake well” and “Refrigerate” and the expiry date which is 60 days after preparation

Appendix 7 Recommendations for administration of Temozolomide

(Patients who are unable to swallow capsules and cannot obtain a suspension)

[figure not shown]
If the patient is unable to swallow capsules, the below instructions or the one in Appendix 5 must be followed for safe administration of temozolomide.

It is necessary to wear suitable protective garb and to perform this procedure in a fume hood.

- Temozolomide can be mixed in apple sauce or apple juice
- Place the apple sauce or apple juice in a disposable container
- Open each capsule required for the daily dose and place the powder in a medicine cup
- Add the whole contents of the medicine cup to either apple sauce or apple juice. The medicine will not dissolve completely if mixing in apple juice so have extra apple juice on hand so you can add it to any remaining powder in the bottom of the cup
- If you need to have additional juice or apple sauce remove your gloves before touching the main container then place new gloves on before adding the additional juice or apple sauce to the medicine. (You do not want to contaminate the main container with any powder that may be on your gloves.)
- Anything that comes into contact with the medicine must be disposable, such as the spoon used for mixing or eating the apple sauce

Appendix 8 Wong-Baker FACES® Pain Rating Scale

Wong-Baker FACES® Pain Rating Scale

©1983 Wong-Baker FACES Foundation. www.WongBakerFACES.org
Used with permission. Originally published in *Whaley & Wong's Nursing Care of Infants and Children*. ©Elsevier Inc.

Instructions

Prior to the naxitamab infusion, the Wong Baker FACES® Pain Rating Scale should be presented and explained to the patient, by informing the patient that each face on the scale represents a person who has no pain, some pain or a lot of pain. The staff who will be asking the patient to rate his/her pain should explain that:

- Face 0 does not hurt at all.
- Face 2 hurts just a little bit.
- Face 4 hurts a little bit more.
- Face 6 hurts even more.
- Face 8 hurts a whole lot.
- Face 10 hurts as much as you can imagine, although you don't have to be crying to have this worst pain.

The rating should be done by asking the patient to choose the face that best depicts the pain they are experiencing.

For details of pain assessment please see Section [9.2.7](#).

Appendix 9 FLACC Behavioral Scale

FLACC Behavioral Scale

Categories	Scoring		
	0	1	2
Face	No particular expression or smile	Occasional grimace or frown, withdrawn, disinterested	Frequent to constant frown, clenched jaw, quivering chin
Legs	Normal position or relaxed	Uneasy, restless, tense	Kicking, or legs drawn up
Activity	Lying quietly, normal position, moves easily	Squirming, shifting back and forth, tense	Arched, rigid, or jerking
Cry	No cry (awake or asleep)	Moans or whimpers, occasional complaint	Crying steadily, screams or sobs, frequent complaints
Consolability	Content, relaxed	Reassured by occasional touching, hugging, or being talked to, distractable	Difficult to console or comfort

Each of the five categories (F) Face; (L) Legs; (A) Activity; (C) Cry; (C) Consolability is scored from 0-2, which results in a total score between zero and ten.

Copyright© 2002, The Regents of the University of Michigan. All Rights Reserved.

FLACC Behavioral Pain Scale

Patients who are awake: Observe for at least 1-2 min. Observe legs and body uncovered. Reposition patient or observe activity, assess body for tenseness and tone. Initiate consoling interventions if needed

Patients who are asleep: Observe for at least 2 min or longer. Observe body and legs uncovered. If possible, reposition the patient. Touch the body and assess for tenseness and tone.

Face

Score 0 point if patient has a relaxed face, eye contact and interest in surroundings
Score 1 point if patient has a worried look to face, with eyebrows lowered, eyes, partially closed, cheeks raised, mouth pursed
Score 2 points if patient has deep furrows in the forehead, with closed eyes, open mouth and deep lines around nose/lips

Legs

Score 0 points if patient has usual tone and motion to limbs (legs and arms)
Score 1 point if patient has increase tone, rigidity, tense, intermittent flexion/extension of limbs
Score 2 points if patient has hyper tonicity, legs pulled tight, exaggerated flexion/extension of limbs, tremors

Activity

Score 0 points if patient moves easily and freely, normal activity/restrictions
Score 1 point if patient shifts positions, hesitant to move, guarding, tense torso, pressure on body part
Score 2 points if patient is in fixed position, rocking, side-to-side head movement, rubbing body part

Cry

Score 0 points if patient has no cry/moan awake or asleep
Score 1 point if patient has occasional moans, cries, whimpers, sighs
Score 2 points if patient has frequent/continuous moans, cries, grunts

Consolability

Score 0 points if patient is calm and does not require consoling
Score 1 point if patient responds to comfort by touch or talk in - 1 min
Score 2 points if patient require constant consoling or is unconsoled after an extended time
Whenever feasible, behavioral measurement of pain should be used in conjunction with self-report. When self-report is not possible, interpretation of pain behaviors and decision-making regarding treatment of pain requires careful consideration of the context in which the pain behaviors were observed.

Each category is scored on the 0-2 scale which results in a total score of 0-10Assessment of Behavioral Score:

0 = Relaxed and comfortable
1-3 = Mild discomfort
4-6 = Moderate pain
7-10 = Severe discomfort/pain

Copyright© 2002, The Regents of the University of Michigan. All Rights Reserved.

